2.3 Historical Information

Historical information elicited will include the following: date of birth, sex, race, ethnicity, cycloplegic refraction, cycloplegic autorefraction (performed within 2 months or at enrollment), prior treatment for IXT, spectacle correction, and use of ADHD and anti-seizure medications.

2.4 Testing at the Enrollment Visit

Initial testing at the enrollment visit should be performed without cycloplegia and with the subject's habitual correction (with spectacles if currently wearing, or without spectacles if not

currently wearing).* Trial frames should NOT be used for testing at the enrollment visit for any reason.

* The exception is a subject wearing spectacles not required by pre-randomization criteria (see section 2.2). This subject can be tested with or without these spectacles, provided visual acuity criteria are still met under the condition in which they are evaluated (see section 2.2).

 There is no specified "waiting" time that needs to occur between measurements, although testing must be performed in the following specified order at the enrollment visit, an exception being that distance visual acuity can be tested either at the start of the visit or at the end of the visit:

- 1. Spectacle Prescription Verification (Lensometry): Prior to performing the enrollment examination, the subject's pre-randomization spectacle correction (if worn) is to be verified using a lensometer.
- 2. Health-Related Quality of Life Questionnaire and Symptom Surveys:
 - A brief survey of symptoms that may be associated with overminus such as headaches, eye strain, and problems with spectacle wear will be administered to the parents of the subjects. Parents are asked to respond to the survey questions based on their observations of their child in the past 2 weeks.
 - A brief survey of intermittent exotropia symptoms will be administered to the child.
 - Health-related quality of life (HRQOL) will be assessed using the following two components of the Intermittent Exotropia Questionnaire (IXTQ). 26,27
 - 1. Child IXTQ: A child questionnaire for children ages 5 years or older to assess how the child feels about his/her eye condition. Children 4 years and younger at the time of enrollment will not complete the child questionnaire.
 - 2. Parent IXTQ: A parental questionnaire to assess how the child's eye condition affects the parent (in all children).

STEPS 3 through 9 must be performed in the specified order by the same study-certified examiner (pediatric ophthalmologist, pediatric optometrist, or certified orthoptist) on the same day.

- 3. Control of the Exodeviation #1:
 - Control of exodeviation will be assessed in the habitual correction at distance and near using a standardized IXT control scale (*see below*).²¹
 - Distance (6 meters) fixing on an accommodative target such as a video or reading optotype letters
 - Near (1/3 meter) fixing on Lang near-viewing stick or similar accommodative target
 The scale below applies to both distance and near separately.
 - Intermittent Exotropia Control Scale
- 1019 5 = Constant Exotropia

- 4 = Exotropia > 50% of the 30-second period before dissociation
 - 3 = Exotropia < 50% of the 30-second period before dissociation
- 2 = No exotropia unless dissociated, recovers in 5 seconds
 - 1 = No exotropia unless dissociated, recovers in 1-5 seconds
 - 0 = No exotropia unless dissociated, recovers in <1 second (phoria)

Not applicable = No exodeviation present

Directions:

Step1: Assessment before any dissociation: Levels 5 to 3 are assessed during a 30-second period of observation; first at distance fixation and then at near fixation for another 30-second period. Both distance and near are assessed before any dissociation (i.e., before step 2, when assessing control scores of 0, 1 and 2). If the subject is spontaneously tropic (score 3, 4 or 5) at a specified test distance, then step 2 (assessment after standard dissociation) is skipped at that specific test distance.

Step 2: Assessment with standardized dissociation: If no exotropia is observed during step 1 (i.e., the 30-second period of observation at the specified test distance), levels 2 to 0 are then assessed as the worst of 3 rapidly successive trials of dissociation:

- 1. An occluder is placed over the right eye for 10 seconds and then removed, measuring the length of time it takes for fusion to become re-established.
- 2. The left eye is then occluded for a 10-second period (second assessment under dissociation) and the time to re-establish fusion is similarly measured.
- 3. A third assessment under dissociation is performed, covering the eye (for a 10-second period) that required the longest time to re-fuse.

The worst level of control observed following the three 10-second periods of occlusion should be recorded. Since the level under dissociation is recorded as the worst of the three assessments, if a score of 2 (>5 seconds recovery) is noted on the first or second dissociation, then subsequent dissociation(s) are not needed.

If the patient has a micro-esotropia by cover test but an exodeviation by PACT, the scale applies to the exodeviation.

- 4. Stereoacuity Testing: Stereoacuity will be assessed with habitual correction (if any) using the Randot Preschool stereotest at near (performed at 40 cm). A specific level of stereoacuity is not required for eligibility.
- 1056 5. Control of the Exodeviation #2 (repeat) (see item #3).
- 1057 6. Cover Test
 - Assessed in primary position at distance (6 meters) and near (1/3 meters) using procedures outlined in the *IXT Testing Procedures Manual*
 - 7. PACT Testing & AC/A Determination:
 - PACT will be assessed in primary gaze and without cycloplegia as follows and using procedures outlined in the IXT Testing Procedures Manual.
 - At distance (6 meters) and near (1/3 meter) in habitual correction
 - AC/A assessment at distance (6 meters) measuring the PACT with the subject wearing -2.00D lenses over his/her habitual correction. The AC/A ratio is calculated by taking the difference between the distance PACT measurements with and without -2.00D lenses and dividing the difference by 2.
 - 8. Control of the Exodeviation #3 (repeat) (see item #3)

1069 9. Assessment of Deviation Throughout Exam

- The nature of the exodeviation will be classified at distance and near as either constant, intermittent, phoric, or no deviation based on observations of the examiner assessing control during the entire examination period from the first assessment of control through the last assessment of control. The nature of the deviation will be recorded as:
 - Constant if a manifest tropia is present 100% of the time during the examination, including during all 3 control tests (score of 5 for each test)
 - Intermittent if a manifest tropia is present (including after dissociation) but not 100% of the time during the entire exam.
 - Phoric if a tropia is not observed at any time but a phoria is present.
 - No deviation if no deviation is present at any time.
- If the child appears to have a constant tropia but shows excellent stereoacuity that may be inconsistent with the diagnosis of constant tropia, the examiner should look over the child's polarized glasses to determine whether the child is indeed constantly tropic (by direct observation with a cover test).
- 10. Distance Visual Acuity Testing: Monocular distance visual acuity testing with the habitual correction and without cycloplegia will be measured using the investigators usual testing procedure.
 - Visual acuity testing method must use optotypes.
 - Visual acuity must be tested using the same testing procedure throughout the entire study.
 - Visual acuity will be recorded as Snellen equivalents in logMAR increments.
 - Visual acuity may be tested at the start of the exam or at the end of the exam (not between steps #3 and #9).

11. Cycloplegic Autorefraction (if available at site):

• If an autorefractor is available at the site, refractive error must be measured with the autorefractor following cycloplegia with 1% cyclopentolate (see cycloplegic refraction below). These measures will be used to determine myopic progression in both groups, but will not be used to assess eligibility or to prescribe spectacle correction during the study. Recorded values will be based on a single measurement by the instrument (which may be a mean of several individual measures, depending on system). The autorefraction should be done on the same day as the cycloplegic refraction, which may be done within 2 months of enrollment.

12. Cycloplegic Refraction:

- A cycloplegic refraction will be performed at the end of the enrollment visit if not done within 2 months of enrollment.
- The cycloplegic refraction used to assess eligibility must be/have been performed 30 to 45 minutes following at least one application of cyclopentolate 1% per investigator's usual dosage and timing routine.
 - The cycloplegic refraction is based on cycloplegic retinoscopy, which may be done with glasses off or as an over-refraction in front of the current spectacles. Subjective refraction is allowed.
 - When an over-refraction of current eye glasses is performed, the reported cycloplegic refraction will be the sum of the current spectacle power and the over-refraction.

13. Additional Clinical Testing:

• Ocular examination as per investigator's clinical routine to rule out ocular abnormality or lens opacity (if not performed within 7 months)

All testing must be performed within 7 days before randomization except where otherwise noted above.

2.5 Confirmation of Eligibility / Timing of Randomization

All testing to assess eligibility for randomization must be performed without cycloplegia and with the subject's current correction (with spectacles if currently wearing or without spectacles if not currently wearing).

Eligibility criteria relating to refractive error and spectacle correction are based upon the cycloplegic refraction done within 2 months of enrollment or at the end of the enrollment exam (for subjects without a prior cycloplegic refraction performed within 2 months of enrollment).

• If all eligibility criteria are met (including appropriate pre-study refractive correction, if required—see section 2.2), the subject should be randomized on the day of enrollment testing (or up to 7 days later).

• If all eligibility criteria are met *other than* the subject needing to be prescribed new prestudy refractive correction or needing a change in pre-study refractive correction (*section 2.2*):

• Prescribe new spectacles paid for by the study

 • Have the subject return for a repeat enrollment exam (paid for by the study) within 1 month and after wearing the new pre-study spectacles for at least 1 week. All enrollment testing except cycloplegic refraction must be repeated.

o If the subject meets all eligibility criteria at the repeat enrollment exam, he/she will be eligible for randomization at that time (or up to 7 days later).

If the subject fails any eligibility criteria at the repeat enrollment exam, the patient is not eligible for randomization and will end study participation.

2.6 Randomization

 Randomization will occur within 7 days after confirming that the subject meets the eligibility criteria.

Subjects entering the study will be randomly assigned with equal probability to one of the following groups:

• Overminus Group

• Non-overminus Group

The Jaeb Center will construct a separate Master Randomization List using a permuted block design stratified by site and baseline distance control. A subject is officially enrolled in the randomized trial when the website randomization process is completed.

Subjects and parents will be masked to the treatment group assignment.

2.6.1 Treatment for Overminus Group

NOTE: Details of spectacles to be prescribed will be automatically calculated by the study website.

No IXT treatment other than the study spectacles specified below can be prescribed at any time during the study unless the subject meets deterioration criteria described in section 3.7.

Enrollment Visit

- Subjects randomly assigned to the overminus group will be prescribed spectacles based on a cycloplegic refraction as follows:
 - o Fully correct the astigmatism in both eyes (if present)
 - Add -2.50D to the sphere component of the cycloplegic refraction for both eyes
- Overminus spectacles are prescribed to be worn all waking hours through the 12-month outcome visit.

12-Month Visit*

- At the 12-month outcome visit, overminus treatment will be discontinued and new nonoverminus spectacles will be prescribed based on the 12-month cycloplegic refraction as follows*:
 - If the cycloplegic refraction is spherical and plano or any amount of hyperopia in both eyes (with no astigmatism and no anisometropia), subjects will wear spectacles with plano lenses in both eyes to maintain masking.
 - Otherwise, fully correct astigmatism in both eyes and prescribe sphere as follows:
 - If least hyperopic eye has SE myopia:
 - Prescribe the full sphere in both eyes
 - If least hyperopic eye has SE hyperopia or emmetropia:
 - Prescribe sphere so that spectacles will have plano SE in the least hyperopic eye
 - Match any reduction of sphere made to the least hyperopic eye in the fellow eye
 - Subjects will wear the new prescription all waking hours until the 18-month visit.

* Unless the subject has already met deterioration criteria confirmed by masked examiner as described in section 3.7 in which case spectacles are prescribed at investigator discretion.

15-Month Visit*

- If the 12-month spectacles for a subject were issued **before** Protocol Amendment II and therefore contain partial-strength overminus (-1.25D), the spectacles should be changed to non-overminus spectacles at the 15-month to discontinue the overminus (see 12-month prescribing above).
- If the 12-month spectacles for a subject were issued **on/after** Protocol Amendment II and therefore are already non-overminus spectacles, the non-overminus spectacles should be continued at the 15-month visit.

* Unless the subject has already met deterioration criteria confirmed by masked examiner
 as described in section 3.7. in which case spectacles are prescribed at investigator
 discretion.

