The Data Safety Monitoring Committee (DSMC) concluded on 10/25/19 that progression of myopia is occurring more frequently in subjects treated with overminus spectacles compared to non-overminus spectacles. Between baseline and 12 months, the mean change in spherical equivalent refractive error at 12 months was -0.42 D (diopter) in the overminus group and -0.05 D in the non-overminus group (difference = 0.39 D P = <.0001). The proportion of subjects whose spherical equivalent refractive error changed by more than 1.00D was 17% in the overminus group (29 of 168); and 2% in the non-overminus group (3 of 146). The DSMC recommended that all subjects active in the full treatment* or weaning phases in both treatment groups be asked to come in for a visit as soon as possible to be given the new information, complete their pending follow-up visit, receive study-paid non-overminus glasses (regular

glasses or no-correction glasses) to be worn through 18 months, and be invited to continue in the study after 18 months to be treated at investigator discretion and to return for visits at 24 and 36 months.

82 83 84

85

86

87

80

81

*Note that the protocol does not require amending the 0 to 12-month on-treatment period in order to discontinue full overminus treatment given that the 37 remaining 12-month visits (as of 11/5/19) were planned to occur by December 2019. These 12-month visits will be completed only slightly early (all subjects have ≥9 months of treatment). As detailed above, non-overminus glasses will be prescribed between 12 and 18 months.

88 89 90

Protocol Change #2

91 92

Original Protocol

93 94 A lens change was required at the 15-month visit in both treatment groups to allow for discontinuation of half-strength (-1.25D) overminus spectacles in the overminus group. The 15-month glasses prescription is the same as the non-overminus group has received throughout the protocol.

95 96 97

Changed Protocol

98 99 100

The 15-month spectacle prescription is the same as in the original protocol (i.e., non-overminus for both treatment groups), but whether a patient needs to receive a change in spectacles at 15 months to achieve this prescription depends on whether their spectacles had been changed to non-overminus at the 12-month visits occurring after Protocol Amendment II.

101 102 103

Section 2.6.1 on treatment in the **overminus** group has been revised as follows:

104

108

109

110

111

112

15-Month*

105 106 107

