- If the 12-month spectacles for a subject were issued **before** Protocol Amendment II and therefore contain partial-strength overminus (-1.25D), they should be changed to nonoverminus lenses at the 15-month visit to discontinue the overminus treatment.
- If the 12-month spectacles for a subject were issued **on/after** Protocol Amendment II and therefore are already non-overminus spectacles, the non-overminus spectacles should be continued at the 15-month visit.

*Unless the subject has already met deterioration criteria confirmed by masked examiner as described in section 3.7, in which case spectacles are prescribed at investigator discretion.

113 114 115

Section 2.6.2 on treatment in the **non-overminus** group has been revised as follows:

116 117

121 122

123

124

125

15-Month*

- 118 • If the 12-month spectacles for a subject were issued **before** Protocol Amendment II and, the 119 non-overminus lenses should be replaced with new non-overminus spectacles at the 15-120 month visit, to maintain masking of treatment groups.
 - If the 12-month spectacles for a subject were issued on/after Protocol Amendment II and therefore are already non-overminus spectacles, the non-overminus spectacles should be continued at the 15-month visit. There is no longer a reason to change the glasses to maintain masking, given that both treatment groups would already be wearing nonoverminus glasses in this situation.
- 126 *Unless the subject has already met deterioration criteria confirmed by masked examiner as 127 described in section 3.7 in which case spectacles are prescribed at investigator discretion.

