128 129 Rationale for Change 130 Whether glasses need to be changed at 15-months depends on when each subject's 12-month glasses 131 were issued, before or on/after Protocol Amendment II. See details in changes to protocol (above). 132 133 **Protocol Change #3** 134 135 Original Protocol 136 Cycloplegic refraction and autorefraction were not performed at the 18-month visit. 137 138 **Changed Protocol** 139 Cycloplegic refraction will be performed at the 18-month visit, and autorefraction will be mandatory if 140 an autorefractor is available at the site (section 3.4). Analysis of 18-month refractive error data was 141 added to section 5.4.1. 142 143 Rationale for Change 144 Given the increased myopia progression in the overminus lens group, the 18-month visit is the first 145 opportunity to assess whether the overminus group continues to have higher myopia than the non-146 overminus group or whether the two treatment groups start to become similar once treatment is discontinued. 147 148 149 **Protocol Change #4** 150 151 Original Protocol 152 Cycloplegic axial length and additional biometry were not measured in the study. 153 154 **Changed Protocol** 155 Cycloplegic axial length, flat corneal radius, anterior chamber depth, and lens thickness (if available) will be measured at 18-months (section 3.4). Analyses for this data are described in 156 section 5.3.1.5 and 5.3.1.6 157 158 159 Rationale for Change 160 Given the increased myopia progression in the overminus lens group, the study is interested in whether 161 axial length also differs between treatment groups. 162 163 **Protocol Change #5** 164 165 Original Protocol Study-paid spectacles (lenses and frame) were provided at the 12-month visit and a change of 166 lenses was provided at the 15-month visit. 167 168 169 Changed Protocol 170 Study-paid spectacles (frames and lenses) will be provided at 12 months, 15 months and 18 months 171 (section 4.7) 172 173 Rationale for Change 174 Paying for a full set of spectacles at the 15-month visit will enable the study to offer a full set of spectacles to all patients coming in for early visits to have treatment discontinued. Study-paid 175

IXT5 Protocol v3.0 (11-22-19)

spectacles will be provided at 18 months now that cycloplegic refraction is being performed to check the spectacle prescription at that time.

178 179

Protocol Change #6

180

- 181 Original Protocol
- The study ends with the 18-month visit.

183

- 184 Changed Protocol (also see next page)

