Engage family and encourage compliance

12-Month On-Treatment Primary Outcome Visit (± 1 month)

- Lensometry
- Health-related quality of life questionnaire and symptom surveys
- IXT control assessment #1(distance and near)
- Randot Preschool stereoacuity at near
- IXT control assessment #2 (distance and near)
- Cover test
- Prism and Alternate Cover Test (distance and near)
- IXT control assessment #3 (distance and near)
- Assessment of control throughout exam
- Distance visual acuity (same method as enrollment)
- Cycloplegic autorefraction (mandatory if available at site)
- Cycloplegic refraction
- ADHD medication use data collection

[figure not shown]
Both Treatment Groups

Overminus: Discontinue Overminus / Prescribe Non-overminus

Non-overminus: Continue Non-Overminus

Based on cycloplegic refraction at 12 months:

- Fully correct astigmatism in both eyes
- Prescribe sphere:
 - If least hyperopic eye has SE myopia:
 - Prescribe full sphere in both eyes
 - If least hyperopic eye has SE hyperopia or emmetropia:
 - Prescribe sphere so that spectacles will have plano SE in the least hyperopic eye
 - Match any reduction of sphere made to the least hyperopic eye in the fellow eye

Assess whether subject has received new spectacles

15-Month Partial-Treatment Outcome Visit (± 1 month)

- Lensometry
- IXT control assessment #1(distance and near)
- Randot Preschool stereoacuity at near
- IXT control assessment #2 (distance and near)
- Cover test
- Prism and Alternate Cover Test (distance and near)
- IXT control assessment #3 (distance and near)
- Assessment of control throughout exam
- Distance visual acuity (same method as enrollment)

If 12-month spectacles were prescribed before Protocol Amendment II, prescribe non-overminus spectacles at 15 months in both treatment groups

If 12-month spectacles were prescribed on/after Protocol Amendment II, continue the same non-overminus spectacles at 15 months

16-Month Phone Call (3 to 4 weeks after 15-month Visit)

Maintain rapport, assess whether subject has received new spectacles (if new were prescribed)

18-Month Off-Treatment Secondary Outcome Visit (± 1 month)

- Lensometry
- Health-related quality of life questionnaire and symptom surveys
- IXT control assessment #1(distance and near)
- Randot Preschool stereoacuity at near
- IXT control assessment #2 (distance and near)
- Cover test
- Prism and Alternate Cover Test (distance and near, distance with -2.00D lens for AC/A)

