3.1 Follow-up Schedule

1262 The follow-up schedule is timed from randomization as follows:

- 1-Month Phone call: 3 weeks (3-4 weeks)
- 3-Month Phone call: 3 months (3-4 months)
- 6-Month Office Visit: 6 months ± 1 month
- 9-Month Phone call: 9 months (9-10 months)
- 12-Month On-Treatment Primary Outcome Visit: 12 months ± 1 month
- 13-Month Phone call: 3-4 weeks following 12-month visit)
- 15-Month Off-Treatment Interim Visit: 15 months ± 1 month
 - 16-Month Phone call: 3-4 weeks following 15-month visit)
- 18-Month Off-Treatment Primary Outcome Visit: 18 months ± 1 month

12721273

1270

Additional visits may be scheduled at investigator discretion.

1274

Subjects with a drop (worsening) of 2 or more octaves from baseline in near stereoacuity during follow-up (*see section 3.7*), confirmed by a retest on the same day, will need to return for an additional retest on a subsequent day.

1278 1279

1280

1281

1282

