5.3.2.1 Mean Distance Control in Baseline Subgroups

- 1800 The treatment group comparisons of 12-month and 18-month distance control will be assessed in
- subgroups based on baseline factors. The specific subgroups of interest include baseline distance
- 1802 control by severity, baseline age group (3 to <7 vs. 7 to <11), use of ADHD medications at any
- time between baseline and the 12-month visit (yes/no), and refractive error level. In accordance
- 1804 with NIH guidelines, subgroup analyses of treatment efficacy according to sex, as well as
- race/ethnicity, will also be conducted.

- 1807 These planned subgroup analyses will repeat the primary analysis, including the baseline factor
- and the baseline factor by treatment interaction. In general, statistical power will be low for
- detection of interactions unless the interaction is very large.

1811 Subgroup analyses will be interpreted with caution, particularly if the corresponding overall analysis does not demonstrate a significant treatment group difference. 1812

1813

1810

1814 5.3.2.2 Mean Distance Control at 18 Months According to Prescribed Weaning Status

- 1815 Of the 355 expected 18-month visits (as of 11/5/19), approximately 283 subjects (80%) will have
- completed a full 3-months of prescribed weaning before discontinuing overminus (or non-1816
- overminus); approximately 35 to 54 (20% to 25%) subjects will have completed partial weaning, 1817
- 1818 and approximately 18 to 37 subjects (5% to 10%) are expected to have no weaning at all, The
- 1819 summary statistics for and distribution of 18-month distance control will be tabulated according
- 1820 to treatment group and full, partial, or no prescribed weaning.

1821 1822

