226 12 months and weaning of overminus between 12 to 15 months. The full cohort analysis
227 will be considered the main secondary analysis. In addition, these analyses will be
228 repeated for the 18-month visit in a sensitivity analysis that will be limited to participants
229 who were prescribed full treatment and weaning, defined as those who completed their
230 15-month visit before Protocol Amendment II discontinuing overminus treatment was
231 approved by the Jaeb IRB on 12/18/19.. If retention of an on-treatment effect is stronger
232 in participants who have full treatment/weaning vs. less than full treatment/weaning, the
233 18-month treatment effect could be diluted in the full cohort analysis vs. the limited
234 cohort.

235

236 **2.2.1 Treatment Group Comparison of Mean 18-month Distance Control**

237 The analyses specified above in Section 2.1 will be repeated using the mean 18-month
238 distance control score. As per the rationale in protocol change #2 of Protocol Amendment
239 I, the 18-month comparison is a secondary analysis, hence no adjustment to alpha (5%)
240 will be made to either the primary or the secondary analyses. It is acknowledged this
241 could inflate the overall type I error rate, i.e. probability of one or more false positive
242 findings, for the analyses of these outcomes.

243

244 The treatment group comparison of mean distance control at the 18-month visit will
245 follow the same modified intention-to-treat principle as specified in Section 2.1.1. To be
246 included in the analysis, the 18-month visit must be completed no earlier than 15 months
247 and no later than 24 months after randomization. If the 18-month visit is not completed
248 within the analysis window, the distance control at the 18-month visit will be imputed
249 using multiple imputation (as specified in Section 2.1.9 above). Eighteen-month data for
250 participants in the overminus group who do not discontinue overminus spectacles
251 according to protocol will be included in analyses and will not be imputed, as will 18-
252 month data from participants in the non-overminus group who start overminus.

253
254
255
256
257
258
259
260
261
262
263
264
265
266
267
268
269
270
271
272
273
274
275
276
277
278
279
280
281
282
283
284
285
286
287
288
289
290
291
292
293
294
295
296
297
298

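### Half-strength overminus ends at a 15-month visit fixed at 15 ± 1 months, yet Amendment II and the weaning counts rely on earlier visits, and the weaned cohort is defined two ways

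*Protocol*

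**What the plan says.** **Treatment and visit sections.** Protocol 2.6.1 deals with children whose 12-month glasses were issued before Amendment II: "partial-strength overminus (-1.25D), the spectacles should be changed to non-overminus spectacles at the 15-month to discontinue the overminus". Change #2 in the amendment text has the same rule: "they should be changed to nonoverminus lenses at the 15-month visit to discontinue the overminus treatment". Section 3.1 schedules the visit as "15-Month Off-Treatment Interim Visit: 15 months ± 1 month". The synopsis (1.16) and flow chart (1.17) give the same window, though both call the visit partial-treatment. A footnote in 1.16 allows for children who formally stopped before the 15-month visit, but sets no rule for those in weaning.

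**Amendment II text.** The Change #1 rationale records the DSMC's recommendation that children in the full-treatment "or weaning phases in both treatment groups be asked to come in for a visit as soon as possible". There they would complete their pending follow-up visit and be given non-overminus glasses. Change #5 treats this as adopted: paying for full spectacles at the 15-month visit lets the study offer them to "all patients coming in for early visits to have treatment discontinued".

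**Analysis sections.** Protocol 5.3.2.2 splits 355 expected 18-month visits into about 283 fully weaned, 18 to 37 not weaned, and a middle group: "approximately 35 to 54 (20% to 25%) subjects will have completed partial weaning". SAP 4.2.2 repeats the figures. SAP 2.2 defines its fully treated and weaned cohort by a 15-month visit completed before Amendment II was "approved by the Jaeb IRB on 12/18/19". Protocol 5.2 and SAP 2.3 and 4.1 instead restrict to children who were prescribed weaning.

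**The concern.** A site working from chapters 2 and 3 would leave a child in half-strength glasses until month 14 at the earliest. A site working from the Amendment II text would bring the same child in at once. The difference is time in overminus after the DSMC had found more myopic change in that arm: 17% (29 of 168) against 2% (3 of 146) with more than 1.00 D.

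Two matters of record follow. An early 15-month visit could be listed as a protocol deviation under section 5.5. An early stop could also be mistaken for the formal discontinuation that section 3.8 restricts.

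The analysis is affected too. The restricted 18-month analysis exists because incomplete weaning might dilute the effect. If partly weaned children enter the restricted cohort under one definition and not under another, the analysis no longer isolates what it was added to isolate.

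**Working it through.** **1. Reproduce the plan's counts** (protocol 5.3.2.2; pending visits from the Change #1 note).

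- Inputs: 355 expected visits; 283 full weaning; 18 to 37 no weaning; 37 twelve-month visits pending on 11/5/19.
- Not fully weaned: 355 − 283 = 72, and 72/355 = 20.3%.
- Partial = 72 − none: 72 − 37 = 35 and 72 − 18 = 54. This matches the printed 35 to 54.
- Likely construction (inferred): 35 children were past their 12-month visit but still in weaning. The upper figure adds 37 − 18 = 19 of the pending children, had they received half-strength glasses before the change took effect.

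**2. Apply 2.6.1 with the 3.1 window as written.** Every child given half-strength keeps it to the 15-month visit, so nobody is stopped early by the amendment.

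| | 5.3.2.2 forecast | 2.6.1 with 3.1 as written |
|---|---|---|
| Weaning to the scheduled 15-month visit | 283 (80%) | 355 − 37 = 318 to 355 − 18 = 337 (89.6% to 94.9%) |
| Stopped early by Amendment II | 35 to 54 | 0 |
| No weaning | 18 to 37 | 18 to 37 |

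The forecast therefore presumes early visits that the treatment and schedule sections do not provide for.

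**3. Timing.** The earliest scheduled stop is 15 − 1 = month 14. Nominal half-strength wear is 15 − 12 = 3 months. With both visits anywhere in their windows it runs from 14 − 13 = 1 month to 16 − 11 = 5 months. Under the early-visit text the stop can come at any point after the 12-month visit.

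**4. Children in half-strength overminus.** The 35 to 54 span both arms. Assuming an even split, 35/2 = 17.5 and 54/2 = 27, so about 18 to 27 children.

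**5. Cohort definitions, by two illustrative children.**

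- Half-strength issued in November 2019, early 15-month visit in January 2020: partial in 5.3.2.2, excluded by SAP 2.2, but included by protocol 5.2 and SAP 2.3 and 4.1, because weaning was prescribed.
- Half-strength issued in late October 2019, early 15-month visit before 12/18/19 (if any took place then): partial in 5.3.2.2, yet counted as fully weaned in SAP 2.2.

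On the plan's forecast, the prescribed-weaning cohort holds 283 + 35 = 318 to 283 + 54 = 337 children, against 283 with full weaning. The size of the SAP 2.2 cohort cannot be derived from the documents.

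**6. Printed percentage.** 35/355 = 9.9% and 54/355 = 15.2%, whereas 20% to 25% of 355 would be 71 to 89. The counts balance; the percentage beside them does not.

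**The case against.** The strongest reply is that there is only one trigger. For a child in weaning, the pending visit is the 15-month visit. A site can bring that visit forward, change the glasses there, and satisfy both 2.6.1 and the amendment text; Change #5 links the two. This stands. A reader might infer that the plan sets two rival stop rules, or that Amendment II orders a stop outside the visit schedule. The documents do not support that: the early attendance is a recommendation quoted in a rationale, and 5.3.2.2 is a forecast. What the reply does not remove is the ± 1 month window and the lack of any early-visit instruction in the operative sections. Nor is this merely an amendment summary differing from later text, since 2.6.1, 3.1, 5.3.2.2 and SAP 4.2.2 are all current.

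Other inferences also go too far:

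- *That the early 12-month visits are equally unprovided for.* The Change #1 note says they will be slightly early with at least 9 months of treatment, and SAP 2.1.1 accepts visits from 270 days. For 15-month visits, SAP 2.3 accepts 12 months onward, but that is an analysis window and does not instruct sites.
- *That 72 to 91 children (20% to 26%) are affected.* Adding 54 to the 37 pending counts 19 children twice; 72 is the ceiling.
- *That the 18-to-37 range shows 19 children turning on ambiguous wording.* It is forecast uncertainty about when visits would fall.
- *That the dates 11/22/19 and 12/18/19 contradict each other.* One is a document date, the other an IRB approval.
- *That no child could have short weaning under the windows.* Step 3 shows that some could, but not as a group timed by the amendment.

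**Conclusion.** The point holds as an inconsistency of wording with consequences for exposure and classification. The 15-month window and the absence of an early-visit instruction conflict with the early attendance that Amendment II describes and that the weaning counts presume. It concerns 35 to 54 children across both arms, about 18 to 27 in half-strength overminus if the arms are even, within at most 72 of 355 (20%) not fully weaned. These are forecasts as of 11/5/19, not observed counts. Whether sites acted differently, and whether early visits were logged as deviations, cannot be known from the documents.

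The date point survives only in small form: 2.6.1 and 2.6.2 split children by issue before or on/after Amendment II without a date. The two cohort definitions are a separate, firm finding. With the last 12-month visits due by December 2019, exposure would have been settled well before the SAP of February 2021. The cohort definition and deviation reporting could still be put right then.

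No view is taken on when half-strength glasses ought to be stopped.

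**What to change.** - Reconcile protocol 1.16, 1.17, 2.6.1, 2.6.2, 3.1 and 5.3.2.2 with the Amendment II text, so that one rule states when children holding half-strength glasses attend and when the glasses are changed. The sponsor and the DSMC choose the clinical rule.
- State whether an early 15-month visit under the amendment is within protocol, so that it is not tabulated as a deviation.
- Give one calendar date separating issue before from issue on/after Amendment II.
- Use one definition of the fully weaned cohort in protocol 5.2 and SAP 2.2, 2.3 and 4.1, and say where partly weaned children go.
- In 5.3.2.2 and SAP 4.2.2, correct the percentage beside 35 to 54 to about 10% to 15% of 355.

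The cost is protocol and SAP wording (a clarification letter or amendment text). No added visits, staff or patients are needed.
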